Our objective is to enroll 64 completers, and we will test the main effects for e-liquid nicotine content, e-liquid flavors, and the interaction in a within-person design. In a within-person design, the power will depend heavily on the intra-participant correlation, which is unknown *a priori*. To evaluate the power, we simulate our trial under various assumptions regarding the effect size for the main effects and interactions, and the within-participant correlation (see Figure below). For the main effects of e-liquid nicotine content and e-liquid flavor, we have 80% power to detect an effect size of approximately 0.45 with a moderate within-participant correlation of 0.4, which ranges from approximately 0.49 with a within-participant correlation of 0.0, to 0.41 with a within-participant correlation of 0.8. For the interaction, we have 80% power to detect an effect size of

approximately 0.65 with a moderate within-participant correlation of 0.4, which ranges from approximately 0.75 with a within-participant correlation of 0.0, to 0.56 with a within-participant correlation of 0.8.

HUMAN SUBJECTS PROTECTION

Recruitment Methods

Participants will be recruited by posting study information on flyers distributed in the community, Craigslist, social media channels, and Wake Forest Baptist's "BeInvolved" site. Members of the PI's research team will perform recruitment. Coordination of potential participants' virtual visits will be done by phone or by email. Contact information will be stored on password-protected computers that are kept behind locked doors for which only the PI's research team will have access keys and passwords.

Recruitment will be continuous through the course of the study. If necessary, advertisements and recruitment strategies will be redesigned to target specific sub-populations if recruitment falls short of a representative demographic balance.

Participants that have previously performed research with the PI and co-investigator research team and have agreed to be re-contacted for future studies may be contacted for recruitment purposes by email or phone according to their previously stated preference.

Informed Consent

Prior to Virtual Visit 1, participants will be briefly screened over the phone to determine initial eligibility. For this process alone, we will seek a waiver of signed informed consent. This part of the research procedure presents no more than minimal risk of harm to subjects and involves no procedures for which written consent is normally required outside of the research context.

Before beginning the informed consent process during Virtual Visit 1, participants will need to show a valid, state issued photo identification. The interviewer will confirm the age and identity of the participant via video (e.g., WebEx, Zoom). The interviewer will then present a PowerPoint via screen share of the main takeaways of the informed consent form. Participants will be asked follow up questions to ensure comprehension of the informed consent form.

In order to ensure adequate informed consent, participants will be asked to read the first several lines aloud to determine literacy. If the interviewer determines that the participant is not literate, they will be dismissed from the study but will receive \$20 for attending the screening visit. The participant will be instructed to read several open-ended questions aloud and discuss the answers with the researcher. Only after the participant and the researcher are fully satisfied that the participant understands the purpose of the study, the confidentiality of the data, the procedures, the risks/benefits and his/her rights as a research participant will the consent form be signed electronically via DocuSign and the participant undergo screening procedures. The participant will be emailed a signed electronic copy of the consent document for their records.

Confidentiality and Privacy

Confidentiality will be protected by collecting only information needed to assess study outcomes, minimizing to the fullest extent possible the collection of any information that could directly identify subjects, and maintaining all study information in a secure manner. To help ensure subject privacy and confidentiality, only a unique study identifier will appear on the data collection form. Any collected patient identifying information corresponding to the unique study identifier will be maintained on a linkage file, stored separately from the data. The linkage file will be kept secure, with access limited to designated study personnel. Following data collection subject identifying information will be destroyed (three years after closure of the study; paper documents will be shredded, electronic documents will be securely deleted using software that will delete and overwrite sensitive disk space), consistent with data validation and study design, producing an anonymous analytical data set. Data access will be limited to study staff. Data and records will be kept locked and secured, with any computer data password protected. No reference to any individual participant will appear in reports, presentations, or publications that may arise from the study.

Data Safety and Monitoring

The principal investigator and co-investigators will be responsible for the overall monitoring of the data and safety of study participants. The principal investigator and co-investigators will be assisted by other members of the study staff.

Potential risks of participation

1. Survey Questionnaires: The interviews will include questions about medical history, tobacco use, and questionnaires about mood. Answering these personal questions could make the participant feel uncomfortable.
2. Breach of Confidentiality: The risk of the interview is loss of privacy if other people find out the results.

3. Smoking Cigarettes: All cigarettes are detrimental to a person's health and can lead to severe or fatal medical problems including:
 - a. Cardiovascular diseases: Coronary heart disease, heart attack, stroke, peripheral vascular disease, reduced blood circulation, abdominal aortic aneurysm
 - b. Respiratory diseases: Emphysema, bronchitis, tuberculosis and chronic airway obstruction
 - c. Cancers: Lung, bladder, liver, colon, cervical, esophageal, kidney, larynx, mouth, pancreatic, throat, stomach cancers and acute myeloid leukemia
 - d. Diabetes
 - e. Abnormal immune function, rheumatoid arthritis
 - f. Other health risks including but not limited to infertility, ectopic pregnancy, lower bone density in postmenopausal women, hip fracture in women, male sexual dysfunction, age-related macular degeneration, blindness and cataracts.
4. Use of Vaping Devices: can exposure users to several chemicals including nicotine, carbonyl compounds, and volatile organic compounds, known to have adverse health effects. The health effects and potentially harmful doses of heated and aerosolized constituents of e-liquids, including solvents, flavorants, and toxicants, are not completely understood. Vaping device aerosol is not harmless "water vapor" although it generally contains fewer toxicants than combustible tobacco products. Specific potential known risks include
 - a. Vaping devices contain nicotine which may contribute to some of the disease associated with smoking
 - b. The most common side effects related to vaping devices are changes in taste, mucus in throat/sinus, dry mouth, dry cough, throat irritation, sore throat, mouth ulcers, dizziness, headache, and nausea.
 - c. On rare occasions, batteries from vaping devices have exploded/ignited and injured users
 - d. Vaping devices can overheat and present minor burn risks if the button is turned on repeatedly. Participants are told to be careful if storing the device in a place where the button might accidentally be pressed often.
 - e. Ingestion of e-liquids containing nicotine can cause acute toxicity and possible death if the content of the cartridges containing nicotine are consumed.
 - f. Participants are told to keep study vaping devices and all e-liquids away from children and pets.
5. Use of Medicinal Nicotine: Most common adverse effects for medicinal nicotine include irregular heartbeat/palpitations, high blood pressure, mouth sores, mouth or throat irritation, heartburn, upset stomach, vomiting, diarrhea, dizzy or lightheadedness, and hiccups or belching. Additional adverse effects associated with nicotine gum include teeth or jaw problems. There may also be a risk of nicotine toxicity including symptoms such as nausea, dizziness, vomiting, diarrhea, and weakness.
6. Dual use of tobacco or nicotine products: There is also the chance of use of more than one product and/or continued use of the products; however, cessation of all tobacco products will be strongly recommended to the participants at the end of the study.
7. Smoking Withdrawal: Participants may experience smoking withdrawal symptoms during this study if they decide not to purchase tobacco products. The symptoms can be uncomfortable but are typically of minimal risk. Smoking withdrawal symptoms include:
 - a. Anger, irritability, frustration
 - b. Anxiousness, nervousness
 - c. Depressed mood or sadness
 - d. Desire or craving to smoke
 - e. Difficulty concentrating

- f. Increased appetite, hunger or weight gain
- g. Insomnia, problems sleeping or waking at night
- h. Restlessness
- i. Impatience
- j. Constipation
- k. Dizziness
- l. Coughing
- m. Dreaming or nightmares
- n. Nausea
- o. Sore throat

8. **Returning to Regular Smoking:** It is possible that if participants return to smoking their usual brand of cigarette at the end of the study they may experience mild and transient nausea, dizziness, and lightheadedness.

9. **Changes in Mood, Emotions and Psychiatric Symptoms:** Smoking and nicotine can affect a person's mood and emotions and are associated with psychiatric disorders including major depressive disorder, general anxiety disorder, bipolar disorder and eating disorders. Any changes in nicotine use or cigarette consumption could adversely affect mood, emotions and the symptoms related to psychiatric conditions in some individuals.

10. **Smoking and Oral Contraceptives in Women:** Women who smoke and are over the age of 35 should not take oral contraceptives that contain estrogen without consulting their physician. Smoking while using oral contraceptives can increase the risk of having a cardiovascular event such as a heart attack or stroke. Additionally, there is a potential risk of thrombosis associated with hormonal therapy (including contraceptives) and smoking.

Avoiding Risks during Pregnancy

Smoking during pregnancy can lead to miscarriage, preterm delivery, stillbirth, birth defects, and other problems. To avoid risks to the participant and fetus, female participants will be tested for pregnancy at the Screening Visit.

Expected benefits of participation

There are no immediate benefits from participating in the study. The information obtained from this study may ultimately help the Food and Drug Administration (FDA) decide how best to regulate tobacco products with the goal of improving public health.

Reporting Unanticipated Problems, Adverse Events or Deviations

Identifying Adverse Events

While participating in the study, adverse events will be assessed at Virtual Visit 6 and carbon monoxide levels from In-Person Lab Visit 3. Adverse events will typically be identified during the administration of the Health Changes Questionnaire. Other adverse events may be identified by spontaneous reports from the participant. Withdrawal symptoms are considered an adverse event if the symptom had a significant impact on the participant's daily life, caused a major disruption of functioning, or took any medication for it.

- **Health Changes Questionnaire:** If the participant answers "YES" to Questions 1, 2, or 3 the interviewer should assess for adverse events.
 1. Have you had any negative changes in your physical or mental health since your last virtual visit? If yes, briefly describe.

2. Since your last virtual visit, have you received any form of medical care? If yes, briefly describe.
3. Have you had any changes in medication since your last visit?

Physiological data that will be reviewed:

1. CO level: The 'Adverse Event Form' will be completed if the average of two (or three) consecutive measurements in the same visit is:
 - o CO is greater than 50 ppm if CO at Screening/Baseline Visit is < 20 ppm.
 - o CO is greater than 60 ppm if CO at Screening/Baseline Visit is 20 – 34 ppm.
 - o CO is greater than 70 ppm if CO at Screening/Baseline Visit is 35 – 49 ppm.

For the participant's protection, participants will be withdrawn immediately from the study if any of the following occur:

1. Cardiovascular disease (CVD) event: Typically includes MI (heart attack), PTCA (angioplasty/stenting), bypass surgery, stroke, peripheral vascular disease (arterial blockages in arms or legs leading to procedure or surgery). Less common CVD problems would be new cardiac arrhythmias (e.g., new atrial fibrillation) or new valvular disease (e.g., mitral or aortic regurgitation).
2. DVT/PE (deep vein thrombosis/pulmonary embolism, i.e., blood clots in the venous system).
3. Suicide Attempt: A participant will be withdrawn if they attempt suicide at any time during participation in the study
4. Psychiatric Hospitalization: A participant will be withdrawn if they are hospitalized for psychiatric reasons at any time during participation in the study.
5. Pregnancy: If a participant indicates they are pregnant at Virtual Visit 6 or In-Person Lab Visit 3, they will be withdrawn from the study, and this event will remain open until delivery. At that time the license medical monitor will contact the participant to ask a few questions about the baby's health and will update the open 'Adverse Event Form'.

The following will be monitored and can lead to the participant being withdrawn by the PI:

1. Expired breath CO >80 ppm
2. Any hospitalization or debilitation in which participation in the study could be detrimental to the recovery process. This will be self-reported by the participant and will be reviewed by the site PI and medical monitor to determine whether continued participation in the study is appropriate.
3. If a participant is behaving in an inappropriate or threatening manner, admits to lying about eligibility criteria, including omitting previous medical diagnoses and medications, is participating in other smoking research studies that could affect the primary outcome measures, does not follow study instructions, etc., then the PI can withdraw them from the study at the PI's discretion.
4. If a participant fails to attend her/his Virtual Visit 1 within the 21-day allowable visit window, they will not be eligible to reschedule the visit or continue participation in the study.

References

http://www.ncbi.nlm.nih.gov/entrez/query.fcgi?cmd=Retrieve&db=PubMed&dopt=Citation&list_uids=10465828
2. Kozlowski, L. T. (2015). Prospects for a nicotine-reduction strategy in the cigarette endgame: Alternative tobacco harm reduction scenarios. *International Journal of Drug Policy*, 26(6), 543-547. doi:10.1016/j.drugpo.2015.02.001
3. Kozlowski, L. T. (2016). Cigarette prohibition and the need for more prior testing of the WHO TobReg's global nicotine-reduction strategy. *Tobacco Control*. doi:10.1136/tobaccocontrol-2016-052995
4. Kozlowski, L. T. (2017). Let actual markets help assess the worth of optional very-low-nicotine cigarettes before deciding on mandatory regulations. *Addiction*, 112(1), 3-5. doi:10.1111/add.13515
5. Shatenstein S. Eliminating nicotine in cigarettes. *Tob Control* 1999;8(1):106; author reply 07-9
http://www.ncbi.nlm.nih.gov/entrez/query.fcgi?cmd=Retrieve&db=PubMed&dopt=Citation&list_uids=10465827

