E-cigarettes have rapidly emerged as a commonly used non-combusted product in the U.S.^{34, 35} with a proposed rule by FDA that it they be deemed a "tobacco product" and regulated as such.³⁶ A study by Hatsukami and colleagues showed that approximately half of all smokers switched to VLNC cigarettes will try e-cigarettes when provided the opportunity and that there is a negative association between smoking VLNC cigarettes and use of alternative products.³⁷ However, we know little about how the characteristics of e-cigarettes impact VLNC use and, conversely, how nicotine reduction in cigarettes impacts the use of e-cigarettes with different characteristics. Both nicotine and non-nicotine factors may be important.

Nicotine. Nicotine delivered via e-cigarettes may serve a variety of functions that support its actions as a reinforcer and an appealing alternative to smoking VLNC cigarettes. Some e-cigarettes can deliver as much or more (among experienced users) nicotine as a traditional cigarette with a relatively rapid rate of absorption (T max < 5 min).³⁸ This pharmacokinetic profile suggests that e-cigarettes may have greater positive reinforcing effects than VLNC cigarettes.³⁹ E-cigarettes can also be used throughout the day to maintain nicotine levels that would otherwise fall by 95% or more once participants start using VLNC cigarettes.⁴⁰ Indeed, e-cigarettes reduce withdrawal symptoms in cigarette smokers,⁴¹⁻⁴⁵ and this suppression is dependent on the nicotine concentration of the e-liquid.⁴⁵ Relatedly, greater nicotine delivery may also result in increased risk of dependence on e-cigarettes.⁴⁶ Finally, nicotine also acts peripherally on receptors in the oropharyngeal cavity which may contribute to sensory effects (discussed below) that might generalize across products. Together, these data suggest that e-cigarettes that more effectively deliver nicotine may be more likely to function as both positive and negative reinforcers and more able to compete with the reduced reinforcing effects of VLNC cigarettes.

Non-nicotine factors. E-cigarettes have a somewhat unique feature relative to other alternative products - they provide sensorimotor stimuli similar to combusted cigarettes, including a smoke-

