2. Self-report smoking at least 5 cigarettes per day for the past year
3. Breathe carbon monoxide (CO) level > 8 ppm or positive urine NicCheck
4. Willingness to use other tobacco products during the study
5. Speak, comprehend, and read English sufficiently to complete study procedures
6. Have home access to a computer, smart phone, or tablet with a web camera and internet access
7. Tried a vaping device at least once in their lifetime

Exclusion criteria:

1. Currently seeking treatment to quit smoking
2. Self-reported serious medical or psychiatric condition(s) including cardiovascular and chronic respiratory diseases
3. Body temperature > 100.4 F

4. Cold, flu or COVID-19 symptoms including fever, cough, and runny nose in the past 30 days
5. Currently pregnant, breastfeeding or intending to become pregnant for the duration of the study or unwilling to agree to use adequate protection to avoid pregnancy
6. CO reading > 80 ppm

Those with unstable medical or psychiatric conditions are excluded as these symptoms could affect a participant's ability to complete the study and how they make decisions about what tobacco products to use. We will exclude those indicating immediate readiness to stop smoking, as participation in this study may not lead to reductions in smoking. We will exclude pregnant people, those trying to become pregnant and those currently breastfeeding due to the potential harmful effects of tobacco use on developing fetuses and infants. Because participants are required to complete portions of the protocol independently during the virtual lab sessions, they will need to be able to independently read and comprehend the study materials.

Those who report past 30 day cold, flu or COVID-19 symptoms will be temporarily excluded as a safety precaution. They will be able to re-screen once they have been symptom-free for more than 30 days.

Telephone Screening Survey

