1. Identifying Information Form will include the participant's Subject Identifier, name, address (including the county of residence), email address, phone number, age, and date of birth.
2. Tobacco Use History and Exposure Questionnaire, which measures variables such as smoking amount, cigarette brand, age of initiation of smoking, number of quit attempts, duration of quit attempts and duration of smoking.
3. Concomitant Medications Form will assess current medication usage.

The following screening surveys will be self-administered via REDCap:

1. Brief Medical History Questionnaire to query current diagnoses, symptoms and past health problems.
2. Demographic History Questionnaire, which will assess age, gender, ethnicity, race, education, income, marital status, living situation, and employment history.
3. Contemplation Ladder³⁴ to assess intention to quit smoking.

Fagerstrom Test for Cigarette Dependence³⁵ (FTCD) to assess nicotine dependence levels. In the event that the REDCap websites are not functioning, the virtual visits will be rescheduled to a later date and time.

Eligibility Determination

Research staff will determine eligibility after reviewing all criteria, sans the expired breath carbon monoxide reading and pregnancy test. Researchers will pay ineligible participants \$20 for their time spent completing the screening surveys. Eligible participants will complete additional surveys and will receive an extra \$10 for their time.

The following baseline assessments for eligible participants will be administered as an interview and entered into REDCap by the interviewer:

1. Timeline Follow Back (TLFB) Questionnaire,³⁶ which will assess past 14-day tobacco and nicotine product use. If a participant's reported cigarette use on the TLFB conflict with their reporting on the Tobacco Use History and Exposure Questionnaire, the RA will point out the discrepancy to the participant and ask whether they would like to modify their responses on the Tobacco Use History and Exposure Questionnaire or clarify why they are discrepant (e.g., participants had an upper respiratory infection in the past week that resulted in atypical smoking behavior).

The following surveys will be self-administered using REDCap:

1. Tobacco Policy Questionnaire (adapted from International Tobacco Control (ITC) – Four Country survey) which assess support for various tobacco control policies, including banning menthol flavoring in cigarettes and e-cigarettes.

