2. Perceived Health Risks Scale, a measure of the perceived addictive potential and other health risks associated with cigarettes, e-cigarettes and nicotine gum
3. Tobacco Product Interest Scale, a visual analog scale assessing interest in use of various tobacco and nicotine products
4. Environmental/Social Influence on Tobacco use to assess environmental and social impacts on tobacco use.

In-Person Lab Visit 1

After completing Virtual Visit 1, participants will complete the COVID screener within 24 hours of their Lab visit via email or phone. Research staff will wear personal protective equipment including face masks and gloves. The participants will be required to wear facemasks when interacting with the staff. If participants do not have a mask, one will be provided to them to use for the remainder of the study. Temperature checks will be conducted immediately upon arrival using a thermal heat scanner.

Participants will provide carbon monoxide (CO) readings at least 6-feet away from other people, including the research staff, while they have their masks off. NicCheck Strips, which assess cotinine levels in urine, will also be used to confirm smoking status if participants have an expired breath CO reading less than or equal to 8 ppm. Participants with child-bearing potential will complete a urine pregnancy test.

The following surveys will be self-administered using REDCap:

1. Minnesota Nicotine Withdrawal Scale a measure of nicotine withdrawal symptoms
2. Questionnaire of Smoking Urges-Brief – Usual Brand Cigarette, which measures the urge to smoke
3. Cigarette Evaluation Scale, which measures responses to cigarettes (e.g., reward, satisfaction)

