Research staff will conduct in-depth interviews with the participants to assess the following constructions: 1) decision-making during the ETM task; 2) use of alternative products during the field assessment; 3) product risk perceptions and; 4) opinions regarding possible tobacco control policies.

In-Person Lab Visit 3

In-Person Lab Visit 3 will be completed up to 48 hours after completing Virtual Visit 6. Participants will complete the COVID screener within 24 hours of their Lab visit via email or phone. Research staff will wear personal protective equipment during the visit including face masks and gloves. The participants will be required to wear facemasks when interacting with the staff. Temperature checks will be conducted immediately upon arrival using a thermal heat scanner. Participants will bring a first void urine sample, which will be banked for future biomarker analysis (e.g., total nicotine equivalents) and all of their used/unused products.

Participants will provide CO readings at least 6-feet away from other people, including the research staff, while they have their masks off. Participants will complete a second iteration of discrete choice task 1. Data from the two choice tasks will be compared within participants to see whether product use affected preferences.

All participants will be emailed a cessation manual and local smoking cessation resources.

Product adherence

To verify self-reported tobacco use, all used and unused products will be collected and counted at In-Person Lab Visit 3. Discrepancies between consumption stated on the TLFB versus consumption based on the products returned will be addressed. Non-adherence (i.e., using products not purchased from the ETM) will be assessed via the TLFB and qualitative interview with the importance of honest self-reporting emphasized. If participants report not using combusted tobacco, then CO readings < 6 ppm will verify their self-report.

Compensation

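### A participant can enter with a CO already below 6 ppm, and for that participant the later CO check on no combusted tobacco use is uninformative

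*Combined protocol and SAP*

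**What the plan says.** Subject Selection Criteria combines two smoking requirements. Inclusion 2 is "Self-report smoking at least 5 cigarettes per day for the past year". Inclusion 3 is "Breathe carbon monoxide (CO) level > 8 ppm or positive urine NicCheck".

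The In-Person Lab Visit 1 section explains when the strip is used. It describes "NicCheck Strips, which assess cotinine levels in urine" and says that they "will also be used to confirm smoking status if participants have an expired breath CO reading less than or equal to 8 ppm". No lower CO limit applies on this route.

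The Product adherence section sets the later rule, applied at In-Person Lab Visit 3: "If participants report not using combusted tobacco, then CO readings < 6 ppm will verify their self-report". It makes no reference to the participant's own CO at Lab Visit 1 or Lab Visit 2, although both are measured. The same section also provides for a count of returned products, a Timeline Follow Back (TLFB) interview and a qualitative interview.

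On other nicotine sources, inclusion 7 is "Tried a vaping device at least once in their lifetime", and the exclusion list does not mention current vaping or nicotine gum use. The background section notes that "Some e-cigarettes can deliver as much or more (among experienced users) nicotine as a traditional cigarette".

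The Analysis Plan lists product use and biomarkers in the field assessment as exploratory. The primary outcome is the number of cigarettes purchased in the marketplace task.

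**The concern.** A cut-off can verify a change only if the person would have failed it before the change. The entry and verification rules were set on different scales: the first accepts either CO or cotinine, while the second uses CO alone. Anyone admitted on cotinine with a very low CO passes the second test on the day of enrolment, while still smoking.

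At stake is what the word verified means when field-week results are reported. The protocol presents the field week as validating the marketplace task, and a report of no combusted use is the clearest sign of switching a participant can give. The background says that more than 75% of participants assigned to very low nicotine cigarettes in trials of six weeks or longer smoked at least one non-study cigarette. That figure does not carry over directly to a one-week assessment, but it shows that the authors expect undisclosed or off-protocol smoking. There is also a financial reason to report none: participants who buy nothing and use no tobacco in the field week are paid their account balance.

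**Working it through.** The plan states no figure to reproduce here. The check sets the two rules against each other and then shows a range for the unknown share.

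**Inputs.** Entry: CO > 8 ppm or NicCheck positive (Subject Selection Criteria, inclusion 3). Upper limit: CO above 80 ppm is excluded (exclusion 6). Verification: CO < 6 ppm (Product adherence). Planned completers: 64 (Power calculation). Assumption: CO is read in whole ppm.

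**Step 1: which entry values already satisfy the later rule.**

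| Lab Visit 1 CO (ppm) | NicCheck negative | NicCheck positive | Already < 6? | Smallest fall needed to reach 5 |
|---|---|---|---|---|
| 0–5 | not admitted | admitted | yes | none |
| 6–8 | not admitted | admitted | no | 6 − 5 = 1, up to 8 − 5 = 3 |
| 9–80 | admitted | admitted | no | 9 − 5 = 4 or more |

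The overlap arises only through the NicCheck route. Without it, the lowest admissible reading is 9 ppm and nobody enters below the verification cut-off.

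**Step 2: what the rule can show.** For an entrant at 0–5 ppm whose smoking and CO do not change, the rule is met with certainty, so it has no power to contradict an untrue report. For an entrant at 6–8 ppm a fall is required, but only of 1 to 3 ppm.

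**Step 3: what confirms smoking at entry for these people.** The strip measures cotinine, which reflects nicotine exposure. Current vaping is not excluded, and the protocol itself says e-cigarettes can deliver cigarette-like nicotine. A positive strip with low CO is therefore compatible with smoking, vaping or both. What remains is self-report: inclusion 2, the tobacco history, and a TLFB "which will assess past 14-day tobacco and nicotine product use". The TLFB is completed by participants already found eligible, and a discrepancy is put to the participant, who may change or explain the earlier answer.

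**Step 4: size.** Let s be the share of completers entering below 6 ppm, r the fraction of them reporting no combusted use, and u the fraction of those reports that are untrue. False verifications, if CO is unchanged, number 64 × s × r × u, which cannot exceed 64 × s. The documents give none of s, r or u. For assumed s:

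| Assumed s | 64 × s | Chance of at least one such entrant, 1 − (1 − s)^64 |
|---|---|---|
| 2% | 1.3 | 0.73 |
| 5% | 3.2 | 0.96 |
| 10% | 6.4 | > 0.99 |
| 20% | 12.8 | about 1.00 |

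So the situation is likely to occur at least once even if rare, but the number of wrong labels may be far smaller than 64 × s.

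**The case against.** The best defence is that CO is one check among several and that little depends on it. Used and unused products are returned and counted, discrepancies with the TLFB are pursued, and an interview follows. The plan defines no CO-verified switching endpoint. Field product use and biomarkers are exploratory and are analysed by regression with adjustment for the corresponding baseline measure, not by classifying people at 6 ppm. Accepting cotinine together with a smoking history is also a legitimate design choice.

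Most of this stands and limits the point. It does not remove it. Counting returned study products cannot reveal cigarettes obtained elsewhere, and the TLFB and interview are self-report. The banked urine is for future analysis, and the example given, total nicotine equivalents, again measures nicotine. CO is the only planned test that responds to combustion, and the stated rule gives a wrong answer for a definable group.

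A reader might infer that smoking is unconfirmed at entry for everyone on the NicCheck route. The documents do not support that: self-reported smoking of at least 5 cigarettes per day is required in addition, and it is cross-checked. What is missing is biochemical confirmation specific to combustion.

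A reader might also infer that the primary result is diluted, on the argument that low-CO entrants are mainly vapers who buy few cigarettes in every marketplace. That needs two undocumented assumptions: that low CO signals mainly vaping, and that such people do not respond to e-liquid nicotine or flavor. They might respond more. Having tried vaping once is not current use, and the purchasing outcome does not use the CO rule.

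**Conclusion.** The point holds in a limited form. For participants whose Lab Visit 1 CO was below 6 ppm while smoking, a Lab Visit 3 CO below 6 ppm carries no information about whether they stopped using combusted tobacco. For those entering at 6 to 8 ppm the evidence is weak, so calling the check void for all NicCheck entrants would go too far.

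The conclusion about the rule follows from the text and needs no assumption beyond a CO that stays about the same when smoking does. The number of people affected does rest on assumption: about 1 to 13 of 64 if 2% to 20% enter below 6 ppm, as an upper bound on false verifications. The consequence lies in how field-week non-use is labelled, in support of exploratory outcomes. No effect on the primary purchasing analysis is shown.

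**What to change.** In the Product adherence section, state that a CO below 6 ppm counts as verification of no combusted use only when the participant's Lab Visit 1 CO was 6 ppm or higher. Report non-use by all other participants as self-reported and not CO-verified. Report how many participants entered by NicCheck with a CO below 6 ppm.

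This takes two or three sentences, needs no new data, excludes nobody and can be applied at analysis. The cost is that a few field-week non-use reports will be labelled unverified, including some that are true. It does not cure the weakness at 6 to 8 ppm, where a fall from 6 to 5 ppm would still count.

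No change to inclusion criterion 3 is proposed. Restricting the NicCheck route to people reporting no other nicotine use would narrow the population and would screen on the same kind of self-report whose reliability is in question.
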